Effect of the treatment on routine lab test. Safety and tolerability of the treatments is the major reason for visits 3 and 4. Major items to be monitored are: hypoglycemia, urinary tract infections, bone fractures, diabetic ketoacidosis and thromboembolic events will be monitored during the follow-up period.

We will also assess survival, re-hospitalizations and heart failure worsening (as more visits, increase in prescription of diuretics, etc)

Frequency of Data Review

Each 6-months or more frequently as needed during the study development.

Rules for Alteration of Study Design

Patients showing any adverse effect (as mentioned before) to the treatments will be advised to stop taking the drug and removed from the trial.

Selection Procedures to Minimize Toxicity

Potential candidates will be screened for eligibility prior randomization. Upon treatment initiation, they will be monitored at 1- and 3- months for presence of adverse effects.

We will also performe a test for safety at study termination.

Grading System to Evaluate Adverse Events

The intensity of clinical AEs will be graded on a 3-point scale (mild, moderate, severe) and will be reported on specific AE pages of the CRF. The three categories of intensity are defined as follows:

- Mild. - The event may be noticeable to the subject. It does not usually influence daily activities, and normally does not require intervention.
- Moderate. - The event may make the subject uncomfortable. Performance of daily activities may be influenced, and intervention may be needed.
- Severe. - The event may cause noticeable discomfort, and usually interferes with daily activities. The subject may not be able to continue in the study, and treatment or intervention is usually needed.

A mild, moderate, or severe AE may or may not be serious. These terms are used to describe the intensity of a

specific event. Medical judgment should be used on a case-by-case basis. Seriousness, rather than intensity assessment, determines the regulatory reporting obligations.

Each AE must be assessed by the investigator as to whether or not there is a reasonable possibility of causal relationship to the study treatment, and reported as either related or unrelated. The determination of the likelihood that the study treatment caused the AE will be provided by the investigator.

Procedures to Assure Data Accuracy

The PI will serve as Investigator of Records (IoR). He will appoint a senior member of his clinical research staff to serve as Study Coordinator, who will work closely with the Regulatory Manager of the Mount Sinai Heart, to monitor case report forms (CRFs) on a weekly basis, and the SMC will meet every 6 months, or more frequently is needed, during the study to review CRFs.

The Study Coordinator will verify data collected on case report forms against source documents. Source documents can include any of the following: hospital records, research records, laboratory values, subject diaries, checklists, pharmacy records, data recorded from automated instruments (such as ECG), medical transcriptions, magnetic media images, and x-rays.

The Study Coordinator will work closely with the Mount Sinai Heart Regulatory Manager to compare the procedures defined in the protocol as well as regulatory requirements to ensure data integrity. Internal auditing includes the review of all the regulatory documents; (IRB, regulatory agency correspondence) and clinical records. The IoR and the Study Coordinator will ensure the following regulatory requirements are met:

- Verify investigator qualifications.
- Review PI and sub-investigator CV's and registrations and verify documentation was current at time of study visit.
- Verify current certifications and lab normal ranges protocol-required procedures.
- Verify equipment not covered under CLIA or CAP certifications are adequately maintained and review certifications.
- Verify facilities remain adequate throughout the trial.
- Ensure drug dispensation and storage complies with regulatory requirements.
- Verify documentation in the master file of receipt of disposition/use and return of product.
- Verify the master file contains guidelines for handling product.
- Verify the site maintains records that indicate product has been supplied only to eligible subjects at protocol specified doses.
- The investigator's records for study drug shipping receipts including lot number and quantity (if applicable).
- Shipping receipts to other sites (if applicable).
- Review of dispensing logs including the subject initials, number, dose or quantity and person dispensing.
- Temperature log.
- Return receipts.
- Verify that the protocol or the master file documents provides the necessary instructions to the patients on how to use, handle, store, and return drug.
- Verify the site is following the approved IRB protocol.
- Ensure protocol deviations and violations are reported.
- Verify Informed Consent process.
- Informed Consent review.
- Review of the signed informed consent documents for the correct version, completeness of the subject's or legally authorized representative signature and date, signature and date of person obtaining the consent, investigator signature and date, and witness name, signature and date when required.
- Documentation of the informed consent process or enrollment note. The staff member should evaluate for documentation of the informed consent discussion, a question and answer period, the subject had adequate time to reflect, make an informed decision, signed the informed consent prior to the initiation of any study procedures and received a copy of the signed informed consent.
- Verify correct version of IRB-approved consent form was used.
- Verify the subject completed a HIPAA form prior to enrollment.
- Verify staff has adequate training and responsibilities have not been delegated to unauthorized individuals.
- Report subject recruiting and enrollment rate.
- Compare the number of subjects who signed informed consent to the limit approved by the IRB.

- Check subject screening log to document subjects who entered screening but did not participate in the trial.
- Verify accuracy of records and completeness of CRF entries and ensure corrections are made when necessary.

Suspension Reported to

Study suspension would be immediately reported to the IRB and the funding agency (Boehringer-Ingelheim) by the PI.

Anticipated Circumstances of Subject Withdrawal

The anticipated circumstances for a subject withdrawal are:

- presence of an adverse event.
- poor adherence to the study.
- any other circumstances based on the opinion of the treating physician.

Primary or Secondary Safety Endpoints

Primary end-point: hypoglycemia, urinary tract infections, diabetic ketoacidosis and thromboembolic events during the follow-up period. Secondary end-points: bone fractures, re-hospitalizations and heart failure worsening (assessed as more visits, increase in prescription of diuretics, etc)

14. Drugs / Biologics

Generic Name

Empagliflozin

Brand Name

Jardiance

Icahn School of Medicine at Mount Sinai (ISMMS) Is the Coordinating Center

Yes

Role of the Investigational Drug Service (IDS)

None

Controlled Substance

No

Drug / Biologic Will Be Supplied By

Sponsor

Using Placebo

Yes

Placebo Will Be Supplied By

Sponsor

Where Drug / Biologic Will Be Administered

Outpatient Faculty Practice Associates (FPA)

Storage Requirements of Drug / Biologic

Controlled Room Temperature (15 - 30°C)

Where Drug / Biologic Will Be Stored

By Research Personnel at a Site Outside of Hospital Areas

ALL of the Following Storage Criteria Are Met

The storage area is well maintained, provides adequate lighting, ventilation, sanitation, space and security. * The temperature in the storage area is controlled and monitored using calibrated monitoring devices. * The temperature monitoring system has sensors for continuous monitoring and alarms set at the points representing the temperature extremes. * Records of temperatures and alarms are maintained and all excursions outside the labeled storage conditions are appropriately investigated and reported to the sponsor.

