2. Any history of diabetes by medical history or by any of the established criteria by the American Diabetes Association. It also includes patients with history of diabetes in remission.
3. ACS or cardiac surgery within the last 3 months.
4. Cancer or any other life-threatening condition.

5. Glomerular Filtration Rate < 30 ml/Kg/min.
6. Use of continuous parental inotropic agents.
7. Systolic BP < 90 mm Hg.
8. Recreational drugs and /or excessive alcohol.
9. Psychiatric disease incompatible with being in study.
10. Any contraindication to MRI procedures.
11. Any other medical or physical condition precluding the subject's participation.

7. Subjects - Participation

Duration of an Individual Subjects Participation in the Study

6 months

Duration Anticipated to Enroll All Study Subjects

20 months

Estimated Date for the Investigators to Complete This Study

3-5 years

Procedures for Subjects to Request Withdrawal

You may stop taking part in this research study at any time without any penalty. This will not affect your ability to receive medical care at any of the Mount Sinai Health System hospitals or to receive any benefits to which you are otherwise entitled.

If you decide to withdraw your consent, we ask that you contact [name] [name], and let him know that you are withdrawing from the study. His mailing address is the Icahn School of Medicine at Mount Sinai, [name]. If you wish to withdraw your authorization as well you must contact [name] in writing at the Icahn School of Medicine at Mount Sinai, [name].

You may also withdraw your permission for the use and disclosure of any of your information for research, but you must do so in writing to the Principal Investigator at the address on the first page. Even if you withdraw your permission, we may still use the already collected information if it is necessary to complete the study. Your health information may still be used or shared after you withdraw your authorization if you should have an adverse event from participating in the study.

Procedures for Investigator to Withdraw Subjects

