The study doctor, the sponsor or the institution may stop your involvement in this research study at any time without your consent. This may be because the research study is being stopped, the instructions of the study team have not been followed, the investigator believes it is in your best interest, or for any other reason. If specimens or data have been stored as part of the research study, they too can be destroyed without your consent.

Participants Will Be Recruited

Yes

Recruitment Method(s)

Clinical Practice, Registry/Bank, Records

How Participants Will Be Identified

In all disclosures outside of Mount Sinai, you will not be identified by name, social security number, address, telephone number, or any other direct personal identifier unless disclosure of the direct identifier is required by law. Some records and information disclosed may be identified with a unique code number. The Principal Investigator will ensure that the key to the code will be kept in a locked file, or will be securely stored electronically. The code will not be used to link the information back to you without your permission, unless the law requires it, or rarely if the Institutional Review Board allows it after determining that there would be minimal risk to your privacy.

Who Will Initially Approach Potential Participants

Treating Physician, Clinic Personnel

How Research Will Be Introduced to Participants

Research will be introduced by the primary physician or physicians from the Heart Failure Program at ISMMS. They will be informed of the significant cardiac benefits obtained in heart failure and diabetic patients. In addition, we will tell the participants that the objective of the study is to investigate whether the benefits seen in the HF and diabetic population could be extrapolated to HF patients independently of their diabetic status.

How Participants Will Be Screened

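### The safety rule ties stopping study drug to leaving the trial, and no section provides a 6-month MRI or later safety follow-up for participants removed under it

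*Combined protocol and SAP*

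**What the plan says.** All references are to the combined protocol and SAP.

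- **Removal rule.** Section 13, under Rules for Alteration of Study Design, sets it out in one sentence: "Patients showing any adverse effect (as mentioned before) to the treatments will be advised to stop taking the drug and removed from the trial". Section 13, Anticipated Circumstances of Subject Withdrawal, also lists "presence of an adverse event".
- **Attribution.** Under Grading System to Evaluate Adverse Events, the investigator judges causality and each event is "reported as either related or unrelated". Section 9 says that investigators are blinded to treatment.
- **Stop-and-call wording.** Section 8 (Risks to Subjects, and the procedures to lessen risk) tells participants to stop the drug and contact the investigators. It does not mention removal.
- **Outcome measurement.** The primary end-point in section 2 is change in LV end-systolic or end-diastolic volume. Section 9 places MRI at visit 2 (baseline) and visit 5 (final) only.
- **Safety follow-up.** Section 13, Specific Items That Will Be Monitored for Safety: "We will also assess survival, re-hospitalizations and heart failure worsening". Section 2, Safety and Tolerability, makes a similar commitment. Section 13, Selection Procedures to Minimize Toxicity, adds: "We will also performe a test for safety at study termination".
- **Analysis.** Section 12, Power Analysis/Data Analysis Plan, names t, Welch and Mann-Whitney tests and a repeated-measures ANOVA. It gives no analysis population and no method for missing values.

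**The concern.** Whether a participant goes on taking the drug and whether the trial goes on observing that participant are separate matters. The rule settles both at once. The participants it takes out are chosen after randomisation by an event judged to be caused by treatment. Section 8 attributes such effects to empagliflozin, so removal may be more frequent on drug. Placebo participants can also be removed, because attribution is blinded.

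Two things are at stake. First, a comparison of those who remain is no longer protected by randomisation if removal is related to LV volume and differs between arms. An MRI that was never acquired cannot be recovered later. Second, reaching one safety end-point can end planned observation for the others, in exactly the participants who had a treatment-attributed effect.

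**Working it through.** **1. What triggers removal.** The phrase in brackets in the rule could point to any of three lists:

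| Effect | Section 2, Safety and Tolerability | Section 8, Risks to Subjects | Section 13, items monitored |
|---|---|---|---|
| Hypoglycemia | yes | yes | yes |
| Urinary infection | yes | yes | yes |
| Ketoacidosis | yes | yes | yes |
| Thromboembolic events, fractures | yes | no | yes |
| Low blood pressure, dehydration, allergy | no | yes | no |

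The scope is therefore unclear. Hypoglycemia, urinary infection and ketoacidosis are on every list, and section 13 makes all three primary safety end-points.

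**2. What follows removal.** The sections on visits, procedures, withdrawal and safety monitoring describe no early-termination MRI, no off-drug visit and no later contact. The safety test at study termination is not assigned to removed participants and is not an outcome MRI. Section 13 lists hospital records as source documents for checking case report forms, with no commitment to search them after removal.

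**3. The plan's own figures.** Section 4 gives 100 to be enrolled and 80 needed to complete, an implied loss of 1 − 80/100 = 20%. The reasons for that loss are not stated. The target of 80 cannot be reproduced, because no effect size, SD or power is given. No removal rate is given either; section 8 says only that the effects are very rare.

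**4. Illustration of bias (all rates and gaps assumed).** Let pA and pB be the fractions removed on drug and placebo. Let g be the amount, in SD units, by which removed patients have a larger volume increase than completers. Assume no true effect, SD 1 and n = 50 per arm.

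- Bias of the completer difference (drug minus placebo) = −(pA − pB) × g. A negative value favours drug.
- SE = √[1/(n(1 − pA)) + 1/(n(1 − pB))].
- Two-sided type I error = Φ(−1.96 − s) + Φ(−1.96 + s), with s = |bias|/SE.

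| pA vs pB | Completers | SE | g | Bias | Type I error |
|---|---|---|---|---|---|
| 5% vs 2% | 47.5 and 49 | 0.2036 | 0 | 0 | 5.0% |
| | | | 0.5 | −0.015 | 5.1% |
| | | | 1.0 | −0.030 | 5.2% |
| 25% vs 15% | 37.5 and 42.5 | 0.2240 | 0 | 0 | 5.0% |
| | | | 0.5 | −0.050 | 5.6% |
| | | | 1.0 | −0.100 | 7.3% |

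If removed patients do better than completers, the sign reverses. If removal is unrelated to LV volume, or is equal and equally selective in both arms, the bias is zero. The second scenario leaves 37.5 + 42.5 = 80 completers, the number in section 4, but nothing says that the allowed loss is due to adverse effects.

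**5. Power cost of keeping follow-up.** Assume a true effect of 0.63 SD, which is what 40 per arm detects with 80% power: (1.96 + 0.84) × √(2/40) = 0.63. Assume also that no effect is kept after stopping and that everyone who stops is followed. The estimated effect becomes 0.63 × (1 − pA). Power is from the noncentral t, two-sided 0.05, with noncentrality = effect/SE.

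| pA vs pB | Follow-up kept, 50 per arm (SE 0.20) | Unbiased completers |
|---|---|---|
| 5% vs 2% | 0.63 × 0.95 = 0.60 SD; 84.2% | 0.63 SD, SE 0.2036; 86.5% |
| 25% vs 15% | 0.63 × 0.75 = 0.47 SD; 64.8% | 0.63 SD, SE 0.2240; 79.3% |

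The completer column is a best case, because it assumes that removal introduces no bias.

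**The case against.** The strongest reply is that the protocol never says follow-up stops. Sections 2 and 13 promise assessment of survival, hospitalisation and heart failure worsening with no exception for removed participants, hospital records are available, and the termination safety test might cover early leavers. This stands in part. It means that a reader should not infer that follow-up is forbidden. The reply is weaker for the MRI, where nothing general or specific offers a substitute for visit 5.

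Second, the rule needs an effect attributed to the treatments, and the withdrawal list in section 13 gives anticipated circumstances, not automatic ones. This also stands: it would be too strong to say that every adverse event leads to removal.

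Third, the effects are described as very rare, and at 5% versus 2% the illustrated distortion is negligible. That is correct. A reader might infer that the primary result will be materially biased, but the documents give no removal rates or outcome gaps to support it.

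Fourth, a reader might see a contradiction with the definition of a severe event: "The subject may not be able to continue in the study, and treatment or intervention is usually needed". That text describes intensity and is not a rule on continuation. A broader removal rule does not contradict it, so the point does not rest on it.

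Fifth, in a pilot mechanistic trial an on-drug question is legitimate. It is, but keeping follow-up leaves both analyses possible, while removal rules out the all-randomised one.

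**Conclusion.** The point holds and should be fixed. The wording of the removal rule is certain. The absence of planned follow-up is an inference from that wording and from the lack of any provision after removal. The firm consequence is missing 6-month LV volumes and unplanned later safety observation in a group selected after randomisation. The consequence for the primary comparison cannot be sized from the documents. On the assumed scenarios with a 1 SD gap it runs from 0.03 SD and 5.2% type I error when removal is rare to 0.10 SD and 7.3% when it is common, and it could be zero or of opposite sign. Because section 12 sets neither an analysis population nor a missing-data method, nothing in the plan limits the effect if removals turn out to be frequent.

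**What to change.** - **Section 13, removal rule.** Separate stopping study drug from leaving the study. Participants who stop drug stay in follow-up for the remaining scheduled visits, including the visit 5 MRI where it can be done, unless they withdraw consent. Say which list of effects the rule refers to.
- **Section 12.** Make the main comparison all randomised participants with data, in their assigned arm. Add a sensitivity analysis for missing visit 5 volumes, for example multiple imputation with arm-specific shifts. An on-drug analysis may be added as supportive. Report drug stops, deaths and missing MRIs by arm, with reasons.
- **Consistency.** Reconcile the removal and withdrawal wording in section 13 with the stop-and-call wording in section 8. When drug should be stopped is for the investigators and is not addressed here.

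The cost is protocol, consent and analysis-plan wording, the remaining scheduled visits, and one MRI per affected participant. No new procedure is needed. The statistical price is dilution. On the assumptions above, power is about 84% instead of 86.5% for unbiased completers at 5% versus 2% removal, and about 65% instead of 79% at 25% versus 15%. The price is small if stopping is rare and material if it is common.
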